### **9.1.2. Macular Edema**

Subjects who developed AEs during the study with one of the following preferred terms will be included in the macular edema summary:

- Macular edema
- Cystoid macular edema

Macular edema start time (in terms of study day) and duration of the AE will be summarized using mean, standard deviation, median, minimum, and maximum by study eye and fellow eye separately. To allow for the computation of simple descriptive statistics, only subjects who develop macular edema during the study will be used for the macular edema start time summary, and only subjects who develop these AEs during the study and later resolved will be used in the duration of AE analysis.

Change from baseline in BCVA at the onset of macular edema, when macular edema is resolved, and at the last visit will be summarized using mean, standard deviation, median, minimum, and maximum by study eye and fellow eye separately. Pseudophakic eyes or phakic eyes at baseline who developed macular edema during the study will be summarized by frequency and percentages separately.

The aforementioned summaries will be performed at the eye level. All macular edema AEs will be provided in a listing.

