**Table 3: Definitions for Treatment Start and End Dates by Treatment Period**

| Treatment Period                    | Treatment Start Date   | Treatment End Date   |
|-------------------------------------|--|--|
| Double-Masked (DM) Treatment Period | The date at which a randomized subject takes the first dose of the DM study drug       | 
The date at which a randomized subject takes the last dose of the DM study drug. If the date of the last dose is missing and the subject does not receive any OL study drug:
 
 
• The day before the Visit 5 (Month 3) date will be considered the treatment end date for subjects who completed the Month 3 Visit
 
• The day before the Exit Visit date will be used for subjects who prematurely discontinued from the study before Visit 5 (Month 3). If the Exit Visit date of a non-completer is not available, then the day before the last available visit date will be considered the treatment end date
 
 |
| Open-Label (OL) Treatment Period    | The date at which a randomized adult subject takes the first dose of the OL study drug | 
The date at which a randomized adult subject takes the last dose of the OL study drug. If the date of the last dose is missing:
 
 
• The day before the Visit 8 (Month 12) date will be considered the treatment end date for subjects who completed the Month 12 Visit
 
• The day before the Exit Visit date will be used for subjects who prematurely discontinued from the study during OL period. If the Exit Visit date of a non-completer is not available, then the day before the last available visit date will be considered the treatment end date
 
  |

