**Table 3: Definitions for Treatment Start and End Dates by Treatment Period (Continued)**

| Treatment Period | Treatment Start Date   | Treatment End Date   |
|------------------|--|--|
| Entire Study     | The date at which a randomized subject takes the first dose of the DM study drug | The date at which a randomized subject takes the last dose of the study drug.
Missing last dose date will be handled the same way as mentioned above. |

Notes:

1. Pediatric subjects only participate in the double-masked period.
2. For each treatment period, the treatment end date will be set to missing if the treatment start date is missing.

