#### 4.1.3. Study Day

The *study day* describes the relative day of an observation starting with the reference date designated as Study Day 1. In this study, the treatment start date is the reference date. Thus, the study day will be calculated as:

- For days prior to the treatment start date, Study Day = Date – Treatment Start Date
- For days on/after the treatment start date, Study Day = Date – Treatment Start Date + 1

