### 9.1. Adverse Events

AEs, SAEs, SARs, serious SARs, and significant AEs (AEs leading to study drug discontinuation and AEs leading to death) will be tabulated by type of AEs by treatment arm using actual treatment received for all AEs, ocular AEs, and non-ocular AEs separately.

Besides the overall AE summary, AEs, SAEs, SARs, serious SARs will be tabulated by SOC and preferred term for all AEs, ocular AEs, and non-ocular AEs separately. A subject who experienced multiple AEs within a SOC or preferred term will be counted only once for that SOC or preferred term. Non-serious AEs (including number of events) and ESIs will also be summarized by SOC and preferred term.

All the AE summaries will be performed for double-masked, open-label, and entire study periods separately. For double-masked period summaries, overall AE summary, summary of AE by SOC and PT, SAEs, SARs, and serious SARs will also be tabulated on pediatric subjects separately. For open-label and entire study period summaries, tabulations by treatment received during double-masked period will be provided as well as overall summary for subjects exposed to DE-117. So, for subjects who exposed to the Timolol arm during the double-masked period, their AE summaries under the Overall DE-117 column will be those AEs that started during the open-label treatment period.

AEs, SAEs, SARs, serious SARs, ocular AEs, AEs leading to death, AEs leading to study drug discontinuation, non-TEAEs, and ESIs, if any, will be listed separately.

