#### 9.1.1. Ocular Inflammation

Subjects who developed AEs during the study with one of the following preferred terms will be included in the ocular inflammation summary:

- Anterior chamber cell
- Anterior chamber flare
- Eye inflammation
- Anterior chamber inflammation
- Iridocyclitis
- Iritis

- Uveitis

Other preferred terms might be added upon review of the AE data before database lock.

Ocular inflammation leading to study drug discontinuation, requiring steroid treatment, or requiring NSAIDs treatment will be summarized at the subject level by frequency and percentage separately.

Ocular inflammation start time (in terms of study day) and duration of the AE will be summarized at the eye level using mean, standard deviation, median, minimum, and maximum by study eye and fellow eye separately. To allow for the computation of simple descriptive statistics, only subjects who develop ocular inflammation during the study will be used for the ocular inflammation start time summary, and only subjects who develop these AEs during the study and later resolved will be used in the duration of AE analysis.

The aforementioned summaries will be performed at the eye level. All ocular inflammation AEs will be provided in a listing.

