### **9.1.3. Cosmetic Change(s)**

Subjects who developed AEs during the study with one of the following preferred terms will be included in the cosmetic change summary:

- Blepharal pigmentation
- Eyelash changes
- Eyelash hyperpigmentation

- Eyelash thickening
- Growth of eyelashes
- Lid sulcus deepened
- Trichiasis
- Iris hyperpigmentation

Other preferred terms might be added upon review of the AE data before database lock.

Cosmetic change(s) start time (in terms of study day) will be summarized using mean, standard deviation, median, minimum, and maximum by study eye and fellow eye separately. To allow for the computation of simple descriptive statistics, only subjects who develop cosmetic change(s) during the study will be used for the cosmetic change start time summary.

The aforementioned summaries will be performed at the eye level. All cosmetic change AEs will be provided in a listing.

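### In the pooled Overall DE-117 column, onset of macular edema, ocular inflammation and cosmetic change is counted from two time origins about 90 days apart

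*SAP*

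**What the plan says.** SAP 9.1.2 reads "Macular edema start time (in terms of study day) and duration of the AE will be summarized", and SAP 9.1.3 reads "Cosmetic change(s) start time (in terms of study day) will be summarized". SAP 9.1.1 uses the same metric for ocular inflammation.

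SAP 4.1.3 gives study day one origin: "In this study, the treatment start date is the reference date". The formula is "For days on/after the treatment start date, Study Day = Date – Treatment Start Date + 1". The Entire Study row of Table 3 defines the treatment start date as "The date at which a randomized subject takes the first dose of the DM study drug". Table 3 also gives the open-label period its own start date: "The date at which a randomized adult subject takes the first dose of the OL study drug". SAP 4.1.3 does not say which of these it means. Table 4 numbers the visits on one unbroken axis through the switch, from Month 3 at Day 91 to Month 12 at Day 361.

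Protocol 7.1 has adults start open-label DE-117 on the evening of Visit 5. SAP 9.1 asks for AE summaries by double-masked, open-label and entire-study period. For the last two it requires tabulation by double-masked treatment and also an overall summary of subjects exposed to DE-117. For subjects who were on Timolol, "their AE summaries under the Overall DE-117 column will be those AEs that started during the open-label treatment period".

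SAP 7.7 obtains the DE-117 exposure of these subjects by subtracting their Timolol days from their total duration on study.

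**The concern.** A column headed Overall DE-117 will be read as describing what happens on DE-117, and its onset row as how long after starting the drug an event appears. For subjects randomized to DE-117, study day answers that question. For subjects who switched from Timolol it does not, because their count includes about three months on the comparator.

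The SAP handles the same feature of the design for two related quantities. Exposure excludes Timolol days (7.7), and the events counted for switched subjects are only those that start in the open-label period (9.1). Onset has no matching rule. A switched subject with macular edema at study day 300 would have been on DE-117 for about 300 − 90 = 210 days.

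Macular edema is an event of special interest because it was reported in earlier DE-117 trials (Protocol 12.1.3). Up to about 200 of the 400 planned adults would switch (Protocol 14.3.1), so these subjects could supply a large part of the pooled column.

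**Working it through.** **Inputs.** Study-day formula: SAP 4.1.3. Treatment start dates: SAP Table 3. Visit 5 at Day 91 ± 7: Protocol 7.4.6 and SAP Table 4. First open-label dose on the evening of Visit 5: Protocol 7.1. The documents give no onset distribution, hazard or event count for these AEs, so the event shares and onset patterns below are assumptions.

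**1. Reproduce the SAP's axis.** Target day ± protocol window gives:

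- Month 3: 91 ± 7 = [84, 98]
- Month 6: 181 ± 10 = [171, 191]
- Month 9: 271 ± 10 = [261, 281]
- Month 12: 361 ± 10 = [351, 371]

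All four match Table 4, as do Week 1 [6, 10] and Week 6 [40, 46]. The count does not restart at the switch.

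**2. Offset for a switched subject.** Let *s* be the study day of the first open-label dose and *d* the day of onset counted from that dose, with the dose day as day 1. Then study day = *d* + (*s* − 1).

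- *s* = 91: offset 90
- *s* = 84: offset 83
- *s* = 98: offset 97

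Macular edema on day 30 of DE-117 is reported as study day 120 (113 to 127). For a subject on DE-117 from the start, *s* = 1 and the offset is 0.

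**3. Effect on the pooled mean.** Shift = 90 × switched subjects' share of events.

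| Assumed share | Shift (days) | Range for offsets 83 to 97 |
|---|---|---|
| 25% | 22.5 | 20.75 to 24.25 |
| 50% | 45 | 41.5 to 48.5 |
| 75% | 67.5 | 62.25 to 72.75 |

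**4. Constant hazard, entire-study summary.** Assume equal arms, no dropout, and 360 days of DE-117 in the original arm against 270 after the switch. Events then split 360/630 = 4/7 and 270/630 = 3/7, with onset uniform within each group.

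- Mean time on DE-117: 4/7 × 180 + 3/7 × 135 = 160.7 days
- Mean study day: 4/7 × 180 + 3/7 × (135 + 90) = 199.3 days
- Within-group variance: 4/7 × 360²/12 + 3/7 × 270²/12 = 4/7 × 10,800 + 3/7 × 6,075 = 8,775
- Between-group variance: 4/7 × 3/7 × 45² ≈ 496. The group means differ by 45 days on either clock (180 against 135, or 180 against 225).
- SD: √(8,775 + 496) ≈ 96 days on both clocks

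The mean moves and the spread does not.

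**5. Early onset.** Assume exponential onset with mean 45 days and equal numbers of events from each group.

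- Mean: 45 becomes 45 + 0.5 × 90 = 90 days
- Median: 45 × ln 2 ≈ 31 becomes 45 × ln(1 + e²) ≈ 96 days
- SD: 45 becomes √(45² + 0.25 × 90²) = √4,050 ≈ 64 days

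Here the spread does grow. The 45-day mean is a chosen value, used only to show direction.

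**6. The other reading of the reference date.** If the open-label start date were the origin in the open-label summary, switched subjects would be timed correctly. An original DE-117 subject with onset at study day 180 would then be shown at 180 − 90 = day 90, despite 180 days on drug. Neither reading gives time on DE-117 for both groups.

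**The case against.** The strongest reply is that nothing is misdated. The SAP promises start time as study day and defines study day, so an event on Day 120 is correctly placed on Day 120. A reader might infer that the SAP records wrong dates for switched subjects; the documents do not support that. Study day is valid as calendar time. It falls short only as a measure of time on DE-117, which the SAP never explicitly says the row is meant to show.

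Several further limits stand:

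- SAP 9.1 also requires tabulation by double-masked treatment. Within each of those columns all subjects share one origin, so nothing is mixed.
- SAP 9.1.1 to 9.1.3 name no columns beyond study eye and fellow eye. That they carry a pooled column is inferred from the parent section.
- Table 4 governs the mapping of visits, not the dating of AEs. It supports the single-axis reading but does not by itself settle which start date 4.1.3 means.
- All these events are listed, so onset could be reconstructed by hand.
- The summaries are descriptive; SAP 6 rules out statistical testing of safety measures.

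A reader might also infer that the mixture always inflates the spread. It does not: under constant hazard the SD is about 96 days on either clock.

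These points narrow the concern to the pooled column. They do not remove it, because that column would still combine two origins and 7.7 shows that the SAP separates Timolol days when it describes DE-117 exposure.

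**Conclusion.** The point holds for the Overall DE-117 column of the open-label and entire-study summaries of ocular inflammation, macular edema and cosmetic change. Followed as written, the column mixes onset counted from the first DE-117 dose with onset counted from the first Timolol dose. The 83-to-97-day range of the offset assumes that Visit 5 falls in its window and open-label dosing starts that evening. The effect on any pooled statistic depends on the unknown share of events from switched subjects and on the onset pattern.

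Double-masked summaries, by-arm columns, pediatric data, incidence and AE duration are not affected, and no efficacy conclusion is touched. The change is still worth making, because it alters the reported onset of an event of special interest and is cheap.

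**What to change.** For the Overall DE-117 column of the open-label and entire-study summaries in SAP 9.1.1 to 9.1.3, summarize onset as AE start date minus the date of the subject's actual first DE-117 dose, plus 1. That date is the first double-masked dose for subjects who received DE-117 in that period, and the first open-label dose for subjects who had received only Timolol before the switch. Key it on actual dosing rather than randomized arm, because safety is summarized by treatment received and SAP 9 groups anyone who took both drugs in the double-masked period with DE-117.

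Events that start on Timolol stay in the Timolol column, timed from the first Timolol dose. Keep study day in the listings and by-arm tables. State in SAP 4.1.3 which of the Table 3 start dates is the reference.

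The cost is one derived variable, one more row or table, and a few lines of SAP text. Table 3 already defines both dates for subjects treated as randomized; a subject given both drugs before Month 3 would need the date from the dosing records. No new data collection is needed.

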12.1.4. Follow-up of Adverse Events

All reported AEs should be followed until resolution or until the subject's participation in the study ends. Subjects with the following types of events should be followed by the Investigator until the event is determined to be resolved, irreversible, chronic, stable, the subject withdraws consent, or no further information can be reasonably obtained.

- On-going SAEs issued after study medication treatment
- On-going ESIs, including pregnancy, medication errors resulting in AE's, and macular edema/cystoid macular edema issued after study medication treatment
- Early termination and withdrawal from the study due to study medication related AEs

In addition, on a case by case basis, Santen (or designee) may request follow up beyond the scheduled exit visit.

The follow-up information on an individual SAE or AE (or ESI) will be entered into the eCRF prior to database lock. If the information requested by Santen is not part of the eCRF, or when database lock has already been completed, the site's response to follow-up requests should be emailed to [contact] or reported in writing and fax to [contact] (in the US).

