**Table 7: Handling of Missing Date for Medical Events and Medications**

| Date  | Type of Missing Date                         | Handling of Missing Date   |
|---|--|--|
| Event onset date
(e.g., YYYY-MM-DD)      | Completely missing                           | No imputation will be applied:
For AE, the event will be considered treatment emergent.
For CM, the event will be considered concomitant.
For MH, the event will be considered to occur prior to Inform Consent date. |
|   | Only YYYY is available                       | Use the first date of YYYY to impute the missing month and day of the onset date.  |
|   | YYYY and MM are available, but DD is missing | Use the first date of MM to impute the missing day of the onset date.  |
| Event resolution date
(e.g., YYYY-MM-DD) | Completely missing                           | No imputation will be applied. The event will be considered ongoing (i.e., not resolved) at the last visit date.   |
|   | Only YYYY is available                       | Use the last date of YYYY to impute the missing month and day of the resolution date.  |
|   | YYYY and MM are available, but DD is missing | Use the last date of MM to impute the missing day of the resolution date.  |

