## 6.5. Interim Analysis

No interim analysis is planned for this study.

Analysis of the double-masked period data will be conducted when all the randomized subjects complete their Month 3 Visit, data cleaned and frozen. All efficacy and safety data from open-label period at the time of this data cut will also be analyzed and reported. The [011709IN Data Cut Plan](#) details how data collected during open-label period will be cut for this “snapshot”.

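### Duration of macular edema and ocular inflammation is summarized only for events that resolved, so the reported mean and median are biased short on average, with no unresolved count beside them

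*SAP*

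**What the plan says.** SAP 9.1.2 plans that macular edema "duration of the AE will be summarized using mean, standard deviation, median, minimum, and maximum by study eye and fellow eye separately". The set is then limited: "only subjects who develop these AEs during the study and later resolved will be used in the duration of AE analysis". SAP 9.1.1 applies the same restriction to ocular inflammation. The reason given is "To allow for the computation of simple descriptive statistics".

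SAP Table 7 leaves a completely missing resolution date unimputed: "The event will be considered ongoing (i.e., not resolved) at the last visit date". Such an event has no duration and falls outside the summary.

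Protocol 12.1.4 sets two lengths of follow-up. The general rule is "All reported AEs should be followed until resolution or until" the subject's participation ends. Ongoing SAEs, ongoing events of special interest (which include macular edema) and withdrawals due to drug-related AEs are followed longer, "until the event is determined to be resolved, irreversible, chronic, stable", or until consent is withdrawn or nothing more can be learned. Follow-up information "will be entered into the eCRF prior to database lock".

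SAP 9.1 to 9.1.2 specify no time-to-resolution analysis, no censored duration and no count of unresolved cases beside the duration figures.

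**The concern.** Whether an event enters the duration summary depends on whether it ended while someone was still watching. Long events are less likely to meet that condition, and irreversible events never do. The protocol foresees such cases: three of the four clinical end states it names for extended follow-up are something other than resolution.

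Macular edema is a named event of special interest, and Protocol 12.1.3 notes that it has been seen in DE-117 trials. SAP section 6 rules out statistical testing of safety measures, so the descriptive figures are the safety evidence. A mean or median duration is easily quoted without its denominator, and nothing printed beside it would show how many cases it leaves out.

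**Working it through.** The documents state no case count, unresolved share or expected duration, so there is no figure of the plan's own to reproduce. The direction follows from the rule. The size is illustrated under stated assumptions.

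**Direction.** Let T be the duration and C the follow-up available after onset. If C is independent of T, then E[T | T ≤ C] ≤ E[T]. An event that never resolves has T effectively infinite and is always excluded.

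**Inputs.** From the documents: the resolved-only rule (SAP 9.1.1, 9.1.2), Month 12 at Day 361 (SAP Table 4) and the two follow-up rules (Protocol 12.1.4). Assumed: exponential durations with true median m = 60, 90 or 120 days, onset uniform over Days 1-361, and follow-up ending L days after Day 361, with L = 0 or 180.

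**Formula.** Let λ = ln 2 / m, with C uniform on (L, L + 360).

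- Share resolved: R = 1 − [e^(−λL) − e^(−λ(L+360))] / (360λ).
- The resolved-only median t solves P(T ≤ t and T ≤ C) = R/2.
- For L = 180 every solution lies below 180 days, so P(T ≤ t and T ≤ C) = 1 − e^(−λt) and t = −ln(1 − R/2)/λ.
- For L = 0 the left side is [t − (1 − e^(−λt))/λ + (360 − t)(1 − e^(−λt))]/360, solved numerically.

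**Worked case, m = 60, L = 180.** λ = 0.01155 and 360λ = 4.159. R = 1 − (0.1250 − 0.0020)/4.159 = 0.970. t = −ln(1 − 0.485)/0.01155 ≈ 57 days.

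| True median | L = 0: resolved | Resolved-only median | Short by | L = 180: resolved | Resolved-only median | Short by |
|---|---|---|---|---|---|---|
| 60 d | 76% | 45 d | 25% | 97% | 57 d | 4% |
| 90 d | 66% | 57 d | 36% | 92% | 79 d | 12% |
| 120 d | 58% | 66 d | 45% | 85% | 96 d | 20% |

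L = 0 matches inflammation events followed only to exit. L = 180 is one possible length of extended follow-up for macular edema; the protocol sets no fixed length. With L = 365 the three medians are 60, 87 and 111 days, so for events that do resolve the bias shrinks as follow-up lengthens.

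**Cases that never resolve.** Suppose, as an assumption only, that 20% never resolve, the rest have median 60 days and follow-up is unlimited. The true median over all cases solves 0.8(1 − 2^(−t/60)) = 0.5, so t = 60 × log2(1/0.375) = 85 days. The resolved-only median stays at 60. Longer follow-up does not remove this part.

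**Earlier data cut.** SAP 6.5 says: "Analysis of the double-masked period data will be conducted when all the randomized subjects complete their Month 3 Visit". Events open at that cut are unresolved by definition. As a limiting case, if observation ended at Day 91 with a mean duration of 60 days and every event resolving eventually, simulation gave a resolved-only median of 19 days against a true 42. Many adults will have been followed past Day 91 by then, so this is a bound.

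**Does Kaplan-Meier repair it?** In the scenario with 20% never resolving and a true median of 85 days, simulation with these cases kept at risk to the end of observation returned 85. Censoring them when they are judged irreversible (assumed between Days 30 and 90) returned 77, because that censoring is informative.

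**The case against.** The strongest reply is that the SAP names its population and its reason openly, and that a median among resolvers is a correct figure for resolvers. That stands: the statistic is a narrow one and is not miscalculated. What is missing is the label and the count that would stop it being read as the duration of all events.

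Second, unresolved cases are not hidden. They remain in the AE and special-interest tabulations, the start-time summaries (which cover every affected case) and the listings. For macular edema, the last-visit BCVA summary is not limited to resolved eyes. Because SAP section 6 includes n in continuous summaries, the start-time n minus the duration n approximates the unresolved count. A reader might infer that the plan conceals irreversible macular edema or presents it as reversible; the documents do not support that. The remaining defect is that the reader must reconstruct the count, and learns nothing from the duration summary about how long unresolved cases had been followed.

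Third, it is tempting to apply the 25% to 45% shortfall to macular edema. That assumes follow-up stops at Day 361, which Protocol 12.1.3 and 12.1.4 do not impose on an event of special interest. The smaller range is the fairer illustration there, plus any cases closed as irreversible, chronic or stable. Extended follow-up can also reach inflammation that is an SAE or leads to a drug-related withdrawal.

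Fourth, not every excluded case is a long one: a late-onset event may be open only because follow-up ended. The bias is downward on average, not case by case.

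**Conclusion.** The point holds for both event types as a bias in a descriptive safety summary. The direction is certain on average if follow-up is independent of duration, and irreversible cases are excluded by rule. The actual size cannot be computed from the documents. Under the stated exponential and uniform-onset assumptions, the resolved-only median is about 25% to 45% short for events followed only to exit and about 4% to 20% short with 180 further days, before any allowance for cases that never resolve; the 20% rate used for those is an assumption. A reader might conclude that the longest cases disappear from the safety report or that the plan's figure is simply wrong. Neither follows: the exclusion affects the duration statistics alone. The change should be made before the analysis is run. Nothing in the primary analysis depends on it.

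**What to change.** In SAP 9.1.1 and 9.1.2:

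- Label the existing summary 'among resolved events'.
- Print beside it, for study eyes and fellow eyes separately, the number and percent unresolved at last contact (ongoing, chronic, stable or irreversible), with their follow-up times.
- Where event numbers allow, add a Kaplan-Meier time to resolution by study eye and fellow eye. Do not pool eyes, because two eyes of one subject are correlated and the SAP already reports them separately. Censor ongoing events at last contact. Keep events judged irreversible or chronic in the risk set as not resolved, for example censored at the end of the observation period and not at the date of that judgement.

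The cost is a few sentences in the SAP and some lines of code on data already collected; Table 7 already defines ongoing status for events with no resolution date. No clinical procedure changes. The drawback is that the Kaplan-Meier median may not be estimable when events are few, in which case the counts and follow-up times stand alone.
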